7.3.1.2 Missing Data at a Disease Assessment

If a subject has missing tumor measurements at some assessment for 1 or more target lesions, the sum of the longest diameters (SLD) will be reported for the remaining target lesions. These data will be used to indicate radiologic disease progression if the SLD for the observed lesions increases at least 20% from the nadir SLD of all lesions, in spite of the missing data (or if other criteria for PD are met). If a subject has missing tumor assessments at some assessment for 1 or more non-target lesions, radiologic disease progression will be determined if at least 1 of the remaining non-target lesions exhibits unequivocal progression (or if other criteria for PD are met). If a subject has missing tumor measurements at some assessment(s) for 1 or more target or missing recorded response at some assessment(s) for 1 or more non-target lesions and criteria for PD are not met, an overall response of non-evaluable will be assigned for the assessment(s).

7.3.1.3 Missing Disease Assessment(s)

If a subject has a completely missed assessment(s) followed by an assessment showing radiologic disease progression, then PD will be assigned at the target date of the first missed assessment following an assessment showing no progression. This target date is defined as 42 days after the previous disease assessment showing no progression. If a subject has a missed assessment(s) followed by an assessment showing no radiologic disease progression, then the assumption will be that the subject remained stable during the missed assessment(s).

7.3.2 Other Censoring Rules

Subjects who reach the survival endpoint due to any reason prior to experiencing a radiologic disease progression will be censored for TTP at the date of their last complete disease assessment. Subjects remaining on study without radiologic disease progression or death at the time of analysis will be censored for TTP and PFS at the date of their last

complete disease assessment. Subjects lost to follow-up prior to experiencing a radiologic disease progression or death will be censored for TTP and PFS at the date of their last complete disease assessment.

7.4 Protocol Prohibited Therapies and Medications

As specified in Section 5.3 of the protocol, subjects should not receive any investigational or noninvestigational cytotoxic chemotherapy, hormonal therapy, biological therapy (including monoclonal antibodies), immunotherapy or any locoregional therapy (such as embolization, radiofrequency ablation (RFA), or percutaneous ethanol injection) to treat hepatocellular carcinoma during the treatment period. Alternative anticancer therapies may be administered after radiologic disease progression has been documented.

7.4.1 Protocol Prohibited Locoregional Therapy

These censoring rules apply to the primary analysis of TTP as well as PFS and disease response endpoints as determined by the BICR. Any locoregional therapy received while on study including embolization, RFA or percutaneous ethanol injection and the date performed will be reported to the BICR. If the BICR reviewer believes that one of the target lesions selected at baseline has been affected by such therapy, and that subsequent response or SD is attributable to locoregional therapy, the BICR reviewer will call that subject non-evaluable at all future disease assessments that occur on or after the date of locoregional therapy. Otherwise, the BICR reviewer will assess the subject ignoring the locoregional therapy.

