Appendix 5 Modified Response Evaluation Criteria in Hepatocellular Carcinoma (mRECIST for HCC)

AM01
21Dec10

(Adapted from [Lencioni](#), 2010 for use in this study)

Measurable disease: The presence of at least 1 target lesion, by contrast enhanced computerized tomography (CT) with use of multislice scanners, or contrast enhanced dynamic magnetic resonance imaging (MRI).

Target lesion: Meets all the following criteria:

- Located in the liver.
- Can be accurately measured in at least 1 dimension.
- Well-delineated area of viable, hypervascular (contrast enhancement in the arterial phase) tumor that is > 2 cm in the axial plane.
- Suitable for repeat measurement.
- Not previously treated with locoregional or systemic treatment unless the lesion shows a well-delineated area of viable (contrast enhancement in the arterial phase) tumor that is > 2 cm in the axial plane. (If the lesion is poorly demarcated or exhibits atypical enhancement as a result of the previous intervention, then it cannot be selected as a target lesion).

A maximum of 5 target lesions may be selected.

Nontarget lesion: Other lesions, including small lesions (≤ 2 cm in the axial plane). Note that malignant portal vein thrombosis should be considered a nonmeasurable, and therefore nontarget, lesion. Lymph nodes at the portal hepatic can be considered as malignant if the lymph node short axis is at least 2 cm. Selection of effusion, including ascites, as a nontarget lesion is prohibited. Similarly, bone lesions or any other lesion outside the CT or MRI of the abdomen or obtained by other modality, may not be selected as nontarget lesions.

Measurement of lesions: Imaging studies will be by contrast enhanced CT, with use of multislice scanners, or contrast enhanced MRI. The same method must be used at baseline and during follow up. Note that the longest diameter of the viable tumor is not necessarily located in the same scan plane in which the baseline diameter was measured. The measurement of the viable tumor diameter should not include any major intervening areas of necrosis. (Please see the HGS1012-C1103 Radiographic Data Collection Manual).

Evaluation of target lesions:

Complete Response (CR): Disappearance of intratumoral arterial enhancement in all target lesions.

Partial Response (PR): At least a 30% decrease in the sum of diameters of viable (enhancement in the arterial phase) target lesions, taking as reference the baseline sum of the diameters of target lesions.

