7.1.2 Primary Efficacy Analyses

The primary analysis will be an estimate of median TTP in each arm using Kaplan Meier methods, reported with 95% confidence intervals, along with testing the hazard ratio for TTP at a 1-sided significance level of 0.10 with a Cox proportional hazards model controlling for the factors stratifying the randomization as covariates.

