7.1.3 Additional Analyses of Time to Progression

While the primary analysis of TTP is based on the BICR determination of radiologic disease progression, additional analysis will be performed.

- An analysis of TTP as determined by the BICR censoring subjects at the date of the last complete disease assessment performed prior to any protocol prohibited medications/therapy as specified in Section 5.3 of the protocol (eg, cytotoxic chemotherapy, hormonal therapy, biological therapy, immunotherapy or locoregional therapy).
- An analysis of TTP based on application of mRECIST for HCC to investigator assessed tumor measurements. In this analysis all subjects will be censored for TTP at the date of the last complete disease assessment performed prior to any protocol prohibited locoregional therapy.

- An analysis of TTP based on application of mRECIST for HCC to investigator assessed tumor measurements censoring subjects at the date of the last complete disease assessment performed prior to any protocol prohibited medications/therapy (eg, cytotoxic chemotherapy, hormonal therapy, biological therapy, immunotherapy or locoregional therapy).

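### Does the reader-judged locoregional-therapy rule in SAP 7.4.1 bias the primary BICR time-to-progression comparison enough to need replacing?

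*SAP*

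**What the plan says.** The primary test is a Cox model adjusted for the stratification factors, "testing the hazard ratio for TTP at a 1-sided significance level of 0.10" (SAP 7.1.2), on progression as read by the BICR.

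SAP 7.4.1 applies to that analysis and to BICR PFS and response. Procedure dates are sent to the BICR. A recipient becomes non-evaluable only when two beliefs hold together. The first concerns the lesion: "If the BICR reviewer believes that one of the target lesions selected at baseline has been affected by such therapy". The second concerns the later reading, and it carries the consequence: "and that subsequent response or SD is attributable to locoregional therapy, the BICR reviewer will call that subject non-evaluable at all future disease assessments". This covers every scan from the procedure date onward. In every other case, "Otherwise, the BICR reviewer will assess the subject ignoring the locoregional therapy".

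SAP 7.1.3 adds further TTP analyses. One is "An analysis of TTP as determined by the BICR censoring subjects at the date of the last complete disease assessment" before any prohibited medication or therapy, and locoregional therapy is among its examples. In the first investigator-measurement analysis, "all subjects will be censored for TTP at the date of the last complete disease assessment performed prior to any protocol prohibited locoregional therapy".

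SAP 7.3.2 supplies the general censoring date: "Subjects remaining on study without radiologic disease progression or death at the time of analysis will be censored for TTP and PFS" at the last complete disease assessment. It uses the same date for loss to follow-up and, for TTP, for death before progression.

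**The concern.** Censoring should not depend on the outcome it censors. Under 7.4.1 it does. A recipient whose next scan shows progression stays in as an event. A recipient whose next scan shows stable disease or response can be removed from the procedure onward, and any later progression is lost as well. In the interval that spans the procedure, the arm with more procedures keeps its failures and drops its non-failures, so its hazard is overstated. The decision also rests on two reader beliefs for which 7.4.1 gives no criteria, and the section names no censoring date. The plan's own additional analyses use rules that do not look at the later scan, so it is fair to ask why the primary analysis does. The one-sided 0.10 test and the headline hazard ratio are what is at stake.

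**Working it through.** **The plan's own figure.** SAP 5.1 claims 80% power with 50 per arm for medians of 5.5 and 8.9 months at one-sided 0.10. If TTP is exponential, HR = 5.5/8.9 = 0.618 and ln HR = −0.481. Required events = 4(1.2816 + 0.8416)²/0.481² = 78, and power at 78 events is 0.80. The claim reproduces, and about 80 events is a reasonable base for what follows.

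**Size of the asymmetry by hand.** Assumptions: no treatment effect, median 5.5 months in both arms, every non-progressing recipient attributed, procedure timing unrelated to progression. Scans are 42 days apart (SAP 7.3.1.3), or 1.38 months. The chance that a progression-free subject progresses in one interval is 1 − 2^(−1.38/5.5) = 0.16.

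- With 10 recipients in one arm, 7.4.1 keeps 10 × 0.16 = 1.6 events whose non-progressing counterparts are dropped. On about 40 events in that arm this is 1.6/40 = 4%, ignoring the small added time at risk. With all 10 in the control arm, HR is about 0.96.
- With 5 recipients it is 0.8 events on about 42, or 1.9%, so HR is about 0.98.

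Simulation agrees: 80.9 primary events under 7.4.1 against 79.3 when every recipient is censored (10 recipients), and 84.2 against 83.4 (5 recipients).

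**From hazard ratio to error rate.** With d events, one-sided error ≈ 1 − Φ(1.2816 + ln(HR)·√d/2). With d = 80, HR 0.98 gives 11.7%, 0.96 gives 13.6% and 1.07 gives 5.7%.

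**Simulated results.** Null effect, medians 5.5 months, 50 per arm, 42-day scans, follow-up 12 to 24 months, 12,000 replicates per scenario. All usage rates are assumed. Cells show HR (one-sided error). Recipients are control vs mapatumumab; a dash means not reported.

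| Scenario | SAP 7.4.1 | Censor every recipient |
|---|---|---|
| 5 vs 5, full attribution | 1.00 (10.2%) | – |
| 5 vs 0, full attribution | 0.98 (11.8%) | – |
| 5 vs 0, half attribution | 0.99 (10.8%) | – |
| 10 vs 0, full attribution | 0.96 (14.3%) | 0.99 (10.5%) |
| 10 vs 0, half attribution, procedure halves the hazard | 1.05 (6.5%) | – |
| 10 vs 0, full attribution, 10% of procedures within 6 weeks before progression | 0.97 (12.6%) | 1.02 (8.7%) |
| 10 vs 0, full attribution, 30% so timed | 1.00 (9.8%) | 1.07 (5.6%) |

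An independent large-sample simulation, which also allowed for deaths, gave 0.98 (11.7%) for 10% vs 0% use and 0.96 (13.7%) for 20% vs 0%, and a shift of at most 0.4% with equal use. When procedures clustered before progression, 7.4.1 was off by about 1 to 2% and censoring before the procedure by about 4 to 9%. A third run (4,000 replicates, 10 vs 0, half of procedures timed near progression) gave 1.02 (9.3%) for 7.4.1 and 1.10 (4.3%) for censoring every recipient.

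**Is timing near progression plausible?** The documents leave a route to it. Protocol 5.3.2 allows other anticancer therapy once radiologic progression is documented. Protocol 6.8 requires central confirmation before treatment stops only when progression is equivocal or rests on new lesions alone. A site can therefore call target-lesion progression and proceed to a procedure before the BICR has called it. Censoring before the procedure would remove just those subjects.

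**Censoring date.** 7.4.1 makes every scan on or after the procedure non-evaluable. 7.3.2 censors subjects without progression at the last complete assessment. Read together, they give the last complete assessment before the procedure, which is also the date 7.1.3 uses.

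**The case for a change.** The strongest case for change does not need the alternative to be less biased in every setting. A rule that censors every recipient is deterministic, carries a stated date, and matches the investigator analysis in 7.1.3. At present a gap between the BICR and investigator results mixes reader differences with rule differences. The additional BICR analysis pools locoregional therapy with systemic drugs, so none isolates the locoregional question. The prohibition covers the treatment period while scans continue afterwards, so some use is likely. Changing the wording would cost little.

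Much of this stands as description. It does not make the swap an improvement. Where procedures follow suspected progression, the replacement discards progressions that the BICR actually observed and moves the estimate further than the present rule does. The asymmetry in 7.4.1 also has a measurement reason. Under Protocol Appendix 5, complete response of target lesions is "Disappearance of intratumoral arterial enhancement in all target lesions", which an embolization or ablation can produce directly. Target-lesion growth of 20%, non-target progression or a new lesion is not readily produced that way. The rule disregards the readings a procedure can falsify and keeps those it cannot. Reader discretion remains, but the study is double-blind and the central read is blinded, so the judgement cannot easily be steered by arm.

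**Conclusion.** The reading of 7.4.1 is correct: censoring in the primary analysis depends on the post-procedure scan and on the reader. The consequence is a shift of roughly 1 to 5% in the hazard ratio, about 2% for each 10-point difference in use, when timing is unrelated to progression. The direction depends on which arm has more use, how often the reader attributes, and whether the procedure works. Equal use gives no material bias. The largest error rate, 14.3%, needs 20% use against none and attribution of every non-progressing scan. That is hard to expect of a prohibited therapy in a double-blind trial, though the documents give no rate to settle it.

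No change follows. Which rule is less biased turns on how procedures are timed, which the documents do not tell us, so replacing the primary rule exchanges one modest bias for another. The BICR analysis in 7.1.3 already shows whether the result depends on the later-scan feature, although it also censors for systemic therapy. The censoring date can be worked out from 7.4.1 and 7.3.2 together. Counts of procedures by arm, or one more sensitivity run, would be useful reporting detail but would not alter the primary result.

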7.4.2 Protocol Prohibited Medications

The primary analysis of TTP as well as PFS and disease response endpoints as determined by the BICR will not be impacted by protocol prohibited medications. Instead, additional analyses as described in Section 7.1.3 will be performed.

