- ¹¹ Adverse Events: (S)AE collection begins with the start of 1st study agent administration. Concurrent medications will be recorded within 28 days prior to Cycle 1 Day 1. For subjects in the Extended Access Phase, only SAEs will be recorded.
- ¹² Disease and α – Fetoprotein (AFP) Assessments: Radiologic and AFP assessments will be performed at the end of every 2 cycles (ie, Cycles 2, 4, 6, etc). For subjects discontinuing treatment prior to documentation of radiologic disease progression, disease assessments will be performed every 6 weeks (\pm 3 days), starting 6 weeks after the previous disease assessment while on study, until radiologic disease progression is documented. If disease progression is based only on new lesions or is equivocal, images will be provided to the blinded, independent reader for confirmation of disease progression. All imaging scans used for disease assessments will be made available for independent radiology review by the Sponsor or designee. For subjects in the Extended Access Phase, disease assessments will be performed as at least every 3 months or as per standard of care, whichever is sooner, until disease progression is documented. Independent radiological review of response or for confirmation of disease progression is not required.
- ¹³ Subjects who discontinue mapatumumab/placebo will complete the current cycle assessments per the study calendar. Subsequently, for subjects in the Extended Access Phase, subjects receiving sorafenib alone will be assessed as per local standard of care and will return at least every 6 weeks for BP monitoring. Serious adverse events will be recorded throughout the study

(concluded)

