7.2.2 Major Secondary Efficacy Analyses

Secondary analyses include estimates, using Kaplan Meier methods, of median PFS and median OS along with associated logrank testing. The hazard ratio will also be estimated for PFS and OS using Cox proportional hazard modeling adjusting for factors stratifying the randomization as covariates. In addition, estimates of overall response rate (CR+PR) and disease control rate (CR+PR+SD) will be reported with 95% confidence intervals and an estimate of the difference in response rates and disease control rates between groups will be reported and tested for significance with a Pearson chi-square test (or Fisher's exact test, as appropriate). The analysis of PFS as determined by the BICR described in this section will be repeated, but with PFS based on application of mRECIST for HCC to investigator assessed tumor measurements. Analyses of TTP as described in Section 7.1.3 will be repeated for PFS. In addition, the analyses of objective response, disease control, time to response and duration of response will be repeated with 2 analyses: 1) with endpoints based on application of mRECIST for HCC to investigator assessed tumor measurements and 2) with endpoints as provided directly by the investigator.

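### SAP 7.4.2 points to 7.1.3 for prohibited medications, but 7.1.3 has no response analysis, so a BICR response recorded after another anticancer drug goes unchecked

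*SAP*

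**What the plan says.** SAP 7.4.2 groups three kinds of BICR endpoint (TTP, PFS and disease response) and says of the last that "disease response endpoints as determined by the BICR will not be impacted by protocol prohibited medications". It then gives the remedy: "Instead, additional analyses as described in Section 7.1.3 will be performed".

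SAP 7.1.3 lists three analyses. The first is "An analysis of TTP as determined by the BICR censoring subjects at the date of the last complete disease assessment" before any prohibited medication or therapy. The other two each begin "An analysis of TTP based on application of mRECIST for HCC to investigator assessed tumor measurements"; one censors at prohibited locoregional therapy, the other at any prohibited medication or therapy. All three are of TTP.

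SAP 7.2.2 makes one extension: "Analyses of TTP as described in Section 7.1.3 will be repeated for PFS". For response it says that "the analyses of objective response, disease control, time to response and duration of response will be repeated with 2 analyses", one from mRECIST applied to investigator measurements and one from outcomes as the investigator reports them.

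Locoregional therapy has its own rule in SAP 7.4.1. If the reader judges that a baseline target lesion was affected and that later response or stable disease is due to the therapy, "the BICR reviewer will call that subject non-evaluable at all future disease assessments that occur on or after the date of locoregional therapy".

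**The concern.** Objective response, disease control, time to response and duration of response are read as evidence of what sorafenib with or without mapatumumab did to the tumor. A response that appears after a different systemic drug is not that evidence. SAP 7.4.2 recognizes the problem and offers a remedy for all three endpoint groups, but the remedy does not exist for response.

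A subject can reach this position. Someone may stop study treatment without progression and still be scanned (Protocol Table 6-1, footnote 12): "For subjects discontinuing treatment prior to documentation of radiologic disease progression, disease assessments will be performed every 6 weeks". SAP section 4 sends all on-study images to the BICR. Protocol Appendix 5 ends the best-response window at disease progression, not at the start of new therapy. SAP 7.2.1 also lets a pending PR or CR be confirmed after intervening stable or non-evaluable assessments, so a response first seen on study treatment could be confirmed after a switch.

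If the arms differ in how often this happens, the difference in response rates is biased and the reported results give no means of judging by how much.

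**Working it through.** **Coverage for prohibited systemic drugs**

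| BICR endpoint | Main analysis | Planned analysis that removes post-drug assessments |
|---|---|---|
| TTP | drug ignored (7.4.2) | yes (7.1.3) |
| PFS | drug ignored (7.4.2) | yes (7.2.2, repeating 7.1.3) |
| Objective response, disease control, time to response, duration of response | drug ignored (7.4.2) | none |

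The two response repeats in 7.2.2 change the data source, not the set of scans. SAP 7.3 has no prohibited-medication rule, and it presents investigator-reported outcomes without missing-data or censoring rules.

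**When a post-drug response can count.** All of these must hold:

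1. The drug starts before progression on the read being analyzed; later responses fall outside the Appendix 5 window.
2. Such use departs from Protocol 5.3.2, which allows other anticancer therapy only after documented radiologic progression.
3. Scans continue after the drug starts.
4. For PR or CR, confirmation follows at least 4 weeks after first documentation (SAP 7.2.1), on scans that may all, or only in part, follow the drug.

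Disease control is less exposed. Stable disease needs 6 weeks from baseline without progression (SAP 7.2.1), and the first scheduled scan is at the end of two 21-day cycles: 2 × 21 = 42 days = 6 weeks. A subject stable at that scan normally qualifies already, so the drug matters mainly if it starts earlier or if that scan is missing or non-evaluable. Duration of response is exposed when the drug starts after the response and delays the progression that ends it.

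**Size.** The only design figure is for TTP (SAP 5.1). Schoenfeld's formula with HR = 5.5/8.9 = 0.618 and one-sided alpha 0.10 gives 4 × (1.282 + 0.842)² / (ln 0.618)², about 78 events, at which power is 80.1%. The stated 80% therefore reproduces on the assumption of about 78 events, but it does not bear on response. What matters here is n = 50 per arm.

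- Shift in one arm's response rate from k misattributed responders: k/50. For k = 1, 2, 3 this is 2, 4, 6 percentage points.
- Bias in the difference between arms: (k in Arm B − k in Arm A)/50. Equal numbers cancel in the difference but still raise both rates.
- The documents give no figure for k. Assuming 5% to 10% of subjects take such a drug before progression, 2.5 to 5 per arm are exposed. Only those who then have a response on the BICR read contribute to k, so this is a ceiling.

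**Effect on the test.** SAP 7.2.2 uses Pearson chi-square or Fisher's exact test and sets no significance level or sidedness for response. Removing one responder, with 50 per arm:

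| Responders, before and after removal | Two-sided p |
|---|---|
| 8 vs 1, then 7 vs 1 (Fisher) | 0.031, then 0.059 |
| 10 vs 3, then 9 vs 3 (chi-square) | 0.037, then 0.065 |
| 13 vs 5, then 12 vs 5 (chi-square) | 0.037, then 0.062 |
| 19 vs 10, then 18 vs 10 (chi-square) | 0.047, then 0.075 |

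These rows were chosen to straddle two-sided 0.05, which is an assumed threshold. At one-sided 0.10, the only level the plan states (for TTP), none crosses. The arms are equal, so the one-sided Fisher p is half the two-sided value: 0.015, then 0.030.

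**The case against.** The strongest reply is that ignoring the drug is a deliberate and coherent treatment-policy choice, stated openly and applied alike to TTP, PFS and response. This stands as a defense of the main analysis. It does not explain the missing sensitivity analysis: the SAP made the same choice for TTP and PFS and still planned one, and 7.4.2 names response among the endpoints it sends to 7.1.3.

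Second, the route is narrow. Need for concomitant anticancer therapy is an exclusion criterion, a subject intolerant of one agent may continue the other, and other therapy is permitted only after documented progression. This also stands, and it limits the likely count. A reader might infer that any response after later therapy is credited to the arm; the Appendix 5 window rules that out once progression has occurred.

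Third, the locoregional rule is a reader's attribution judgment about an affected target lesion; otherwise the therapy is ignored. Dropping every post-drug scan would be stricter. That is a reason to make the restricted analysis a sensitivity analysis rather than a replacement. A reader might go further and make pre-drug scans the main derivation. The documents do not support that: it would reverse the SAP's own order for TTP and PFS, and requiring confirmation before the drug could discard a response that began on study treatment.

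Fourth, concomitant medications are tabulated and listed (SAP 6.5), so affected subjects could be found. That shows who took a drug, but not what the response results would be without the later scans.

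**Conclusion.** The gap is real: for four secondary endpoints the SAP refers to an analysis it does not contain, and following its rules credits post-drug responses with no planned check. Each affected responder is worth 2 percentage points in an arm of 50. The number affected is unknown and probably small, since it requires a protocol deviation before progression on the BICR read.

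Two stronger inferences should be avoided. One is that a single subject would flip the planned response test; that rests on a two-sided 0.05 threshold the SAP never sets for response. The other is that one extra responder would double the control rate. The 2% PR rate in Protocol 1.5 comes from another sorafenib trial, published in 2008, while this trial uses mRECIST criteria proposed in 2010 that count vascularity changes, so the rate may not transfer.

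The primary TTP analysis is not in question. This is an inexpensive improvement to secondary endpoints and is worth making before unblinding.

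**What to change.** Keep the all-scans BICR response analysis as the main one. In SAP 7.2.2 add, and in 7.4.2 cite, a sensitivity analysis of BICR objective response, disease control, time to response and duration of response with these rules:

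- Use only assessments before the first prohibited anticancer medication. Say anticancer explicitly, because Protocol 5.3.2 also prohibits strong CYP3A4 inducers.
- Keep affected subjects in the denominator, as SAP 7.3 does for non-evaluable subjects.
- Censor duration of response at the last complete assessment before the drug, as 7.1.3 does for TTP.
- State in advance how a response first seen before the drug but confirmed after it is counted. Treating it as unconfirmed biases the rate down; accepting the later scan lets the other drug contribute.

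Report the result beside the main analysis, with the number of affected subjects per arm. Leave 7.4.1 as it is.

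The cost is one derivation rule and one extra set of tables. The medication dates are already needed for 7.1.3, so no new data are required. The response rate in the sensitivity analysis may be slightly lower.
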